Based on our pilot study,²⁴ we estimate about 80% attendance at the sessions among health system employees. To maximize attendance, we will work with clinics to find a convenient session time (e.g., at an existing meeting). Each attendee will complete a brief pre- and post-test survey (see Appendices). Using items based on those from our pilot study,²⁴ surveys will assess: demographics (pre- survey only); knowledge, attitudes, and beliefs about cervical cancer and HPV self-testing (pre- and post-surveys); and satisfaction with the session (post- survey only). The resulting survey data will be used in evaluation. Surveys will be either written (for in-person sessions) or online (for virtual sessions), with survey items being identical for the two modes of administration. For online surveys, an introduction email (see Appendix) will be sent to healthcare providers to link them to their surveys.

Year 1 Randomized Trial Activities

Baseline Screening Rates and Patient Identification

We will work with the health systems to use their EHR systems to obtain baseline cervical cancer screening rates and identify potentially eligible women. Participation will be limited to one woman per household. Eligibility criteria will include:

- a) female;
- b) ages 30-64 (64 will be the upper age limit instead of 65 so women do not age out of the cervical cancer screening guidelines);
- c) not within recommended cervical cancer screening guidelines for women in this age range (i.e., no Pap test in last 3 years or clinic-based HPV test in last 5 years);
- d) resident of an Appalachian county or patient at a health system in an Appalachian county;
- e) not currently pregnant;
- f) intact cervix;
- g) no history of invasive cervical cancer;
- h) seen in a participating clinic/health system in last 2 years (i.e., active patient); and
- i) have a working telephone.

During this process involving EHRs, members of the project team will not have access to any identifying information (including contact information) of the patients. All communication between the project team and clinics about participants will involve only ID numbers. All identified women will be entered into a database by clinic staff (see Appendix).

Cervical Cancer Screening Reminder Letter

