We will next mail all identified potentially eligible women a standard reminder letter to get a clinic-based cervical cancer screening test (e.g., Pap test) (see Appendix). The letter will indicate that, according to EHR, they are due for a clinic-based cervical cancer screening test and encourage them to contact their clinic to schedule a test (contact information for the clinic will be provided). All letters will appear on clinic/health system letterhead and be signed by a clinic representative. Many health systems have utilized this type of reminder letter for cervical cancer screening,³⁶ so it can be considered "usual care." We think it is important that all potentially eligible women receive this letter that encourages clinic-based cervical cancer screening test before any HPV self-tests are sent. The clinics will mail all of the reminder letters to women. Members of the project team will not have access to any identifying information (including contact information) of the patients. All communication between the project team and clinics about patients will involve only ID numbers.

We will allow about 4-5 months for women who are sent a reminder letter to receive a clinic-based cervical cancer screening test. At the end of the this time period, we will work with the clinics/health systems and use EHR to

identify women who received a clinic-based cervical cancer screening test since the reminder letters were sent. Any woman who has received a test will not continue in the project, as they are no longer unscreened/underscreened. Based on the mean effect size of past studies of mailed cervical cancer screening reminder letters, we anticipate that only about 5% of women who are sent a reminder letter will receive a clinic-based test during the 4-5 month period.³⁶

Randomization

Health systems will be randomized to one of two treatment groups (Group 1 or Group 2) for the cervical cancer prevention program (Figure 1). A 1:1 allocation scheme stratified by state will be used (i.e., five systems per treatment group). Health system will be the unit of randomization. All clinics in a health system will be in the same treatment group.

Year 2 Randomized Trial Activities

[figure not shown]
Group 1: Early Intervention

Group 1 clinics/health systems will receive Early Intervention during Year 1, including HPV self-test devices sent to women (patient-level component) and PN (system-level component). Figure 2 provides an overview of these components.

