HPV Self-Test Distribution and Return

Women in Group 1 clinics/health systems who did not get a clinic-based cervical cancer screening test in the 4-5 months after the reminder letter will be on a sampling frame to receive an HPV self-test. We will randomly sample from this list, stratified by clinic. We will sample a total of 600 women across Group 1 health systems. Sampled women will first be sent a letter (see Appendix) asking them to confirm their eligibility criteria (as defined above). If women meet any criteria that would make them ineligible, they will be asked to indicate this information and return the letter in a provided postage-paid return envelope. Return of a letter will be considered consent for providing this information. Women who return their letter and are found to be ineligible will not continue in the project, and a potential replacement will be randomly sampled from the remaining list (who will then be sent a letter to confirm eligibility). Women who do not return a letter will be considered as confirmed eligible since only women who meet criteria making them ineligible will be asked to return their letter. The clinics will mail all of the reminder letters to women. Members of the project team will not have access to any identifying information (including contact information) of the patients. All communication between the project team and clinics about patients will involve only ID numbers.

Figure 2. Overview of the HPV Self-Testing and Patient Navigation Processes

Each woman who is confirmed eligible will next be mailed an HPV self-test. Self-tests will be sent by mail by the clinics, as members of the project team will not have access to any identifying information (including contact information) of the patients. All communication between the project team and clinics about participants will involve only ID numbers. Women will be sent the HPV self-test free of charge, and the subsequent HPV testing will also be free of charge to women.

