Women in Group 2 clinics/health systems who did not get a clinic-based cervical cancer screening test in the 4-5 month period following the reminder letter being sent will be on a sampling frame to continue with usual care. We will randomly sample from this list, stratified by clinic. We will sample a total of 600 women across all Group 2 health systems. Similar to sampled women in Group 1, sampled women in Group 2 will first be sent a letter (see Appendix) asking them to confirm their eligibility criteria (as defined above). If women meet any criteria that would make them ineligible, they will be asked to indicate this information and return the letter in a provided postage-paid return envelope. Return of a letter will be considered consent for providing this information. Women who return their letter and are found to be ineligible will not continue in the project, and a potential replacement will be randomly sampled from the remaining list (who will then be sent a letter to confirm eligibility). Women who do not return a letter will be considered as confirmed eligible since only women who meet criteria making them ineligible will be asked to return their letter. The clinics will mail all of the reminder letters to women. Members of the project team will not have access to any identifying information (including contact information) of the patients. All communication between the project team and clinics about patients will involve only ID numbers.

Each woman who is confirmed eligible will next be mailed an additional reminder letter to get a clinic-based cervical cancer screening test (i.e., usual care continued; see Appendix) and an information sheet about cervical cancer (the same information sheet that will be sent to Group 1; see Appendix). These materials will be sent by the clinics,

as members of the project team will not have access to any identifying information (including contact information) of the patients. All communication between the project team and clinics about participants will involve only ID numbers.

Data Collection for Year 2

There will be two data collection activities at during Year 2: a medical record review and a patient satisfaction survey.

Medical Record Review

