We will work with the each health system to gather data from EHR. For women in Groups 1 and 2, we will confirm whether any received a clinic-based cervical cancer screening test during Year 2. For women in Group 1 who tested positive for a high-risk HPV type based on their self-test, we will also confirm: a) any follow-up appointment attended; b) any follow-up care received (e.g., Pap test, colposcopy, etc.); and c) any cervical abnormalities (precancerous and cancerous) found during this follow-up. During this process involving EHRs, members of the project team will not have access to any identifying information (including contact information) of the patients. All communication between the project team and clinics about participants will involve only ID numbers. This information will be entered into a database by clinic staff (see Appendix).

Patient Satisfaction Survey

All women who were sent an HPV self-test during Year 2 (i.e., Group 1) will be sent a patient satisfaction survey about HPV self-testing (see Appendix) and an introductory letter about the survey (see Appendix). The survey will be sent to both self-test returners and non-returners. The clinics will mail all of the surveys to participants, with each survey containing the participant's unique ID number. Members of the project team will not have access to any identifying information (including contact information) of the patients. All communication between the project team and clinics about participants will involve only ID numbers.

The survey will examine women's decisions/experiences with their self-test and PN (if applicable), as this information will be valuable in evaluating the intervention. The survey will assess reasons for returning or not returning the self-test, satisfaction with the self-test (appearance, usability, etc.) and its instructions (appearance, readability, etc.). For women who received PN, the survey will assess their satisfaction with PN. Women will be provided with a postage-paid return envelope, and survey return will be considered consent. Women will be sent a \$25 gift card for returning the survey (see Appendix for letter that will be sent with the gift card).

Year 3 Randomized Trial Activities

Group 1: Bundling

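### No EHR re-check is described between building the sampling frame and mailing, so a clinic test in that gap removes a woman who returns the eligibility letter but can count as a success for one who stays silent

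*Combined protocol and SAP*

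**What the plan says.** All places are in section 3 (Methods) of the combined protocol and SAP.

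- **Eligibility criterion c** (Baseline Screening Rates and Patient Identification): a woman must be "not within recommended cervical cancer screening guidelines for women in this age range".
- **EHR check** (Cervical Cancer Screening Reminder Letter): "At the end of the this time period, we will work with the clinics/health systems and use EHR to" find those tested since the letter went out. The reason for removing them is given: "Any woman who has received a test will not continue in the project, as they are no longer unscreened/underscreened".
- **Eligibility letter** (HPV Self-Test Distribution and Return): "Sampled women will first be sent a letter (see Appendix) asking them to confirm their eligibility criteria (as defined above"). Criterion c is therefore among the criteria covered.
- **Reply**: "Women who return their letter and are found to be ineligible will not continue in the project, and a potential replacement will be randomly sampled". The replacement is then sent her own letter.
- **Silence**: "Women who do not return a letter will be considered as confirmed eligible since only women who meet criteria making them ineligible will be asked" for a reply. The next step described is mailing the kit (Group 1) or the second reminder (Group 2). The Group 2 section repeats the same procedure.
- **Outcome** (Data Collection for Year 2, Medical Record Review): for both groups, "we will confirm whether any received a clinic-based cervical cancer screening test during Year 2". Under Aim 1, Measures, any clinic-based test makes a woman screened, whether or not she returned a self-test. Neither place requires the test to follow her mailing.

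**The concern.** Sampling, the letter, the wait for replies, replacement draws and the replacements' letters all come after the only EHR check described before mailing. A woman tested in that interval no longer meets criterion c. Whether she is excluded or counted as a primary-outcome success depends on whether she posts a letter back. The plan's own reason for removing tested women at the frame applies to her equally, but it is enforced only if she replies.

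A retained gap test is not a response to the kit or to the second reminder. Such tests add a similar number of successes to both arms. They make up a larger share of successes where the screening rate is lower (Group 2), and so pull the odds ratio, the planned effect measure, toward 1. Replacement women, who are drawn later, have the longest gap.

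**Working it through.** **Inputs from the plan.** 600 women per arm in Year 2; five health systems per arm; two-sided alpha 0.05; ICC 0.017 (given as an upper limit); 30% vs 10% screened; about 5% tested in the 4–5 months after the first reminder.

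**Assumptions.** Equal system sizes (600/5 = 120 women). The 5% rate carries forward into the gap. Every gap-tested woman is silent and her test counts in Year 2. The 30% and 10% already include gap tests. Replacements have the same screening rate as the women who remain. The gap length is not given, so 1 and 3 months are shown.

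**1. The plan's own power figure.** Design effect = 1 + (120 − 1) × 0.017 = 3.023. Effective n = 600/3.023 = 198.5 per arm. SE = √[(0.3×0.7 + 0.1×0.9)/198.5] = 0.0389, and 0.20/0.0389 = 5.14. Power is 99.9% (normal), 99.4% (noncentral t, 8 df) or 98.1% (5 df, allowing for state strata). The stated floor of 90% is met.

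**2. Planned odds ratio.** (0.30/0.70)/(0.10/0.90) = 3.86.

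**3. Share tested in a gap of k months.** g = 1 − 0.95^(k/4) if the 5% accrues over 4 months, or 1 − 0.95^(k/5) if over 5.

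**4. Rates once gap-tested women are removed and replaced in both arms.** (p − g)/(1 − g). For k = 1 on the 4-month basis, g = 0.0127. Group 1: (0.30 − 0.0127)/0.9873 = 29.1%. Group 2: (0.10 − 0.0127)/0.9873 = 8.8%.

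| Gap | 5% accrues over | g | Women per 600 | Group 1 | Group 2 | Difference (points) | OR |
|---|---|---|---|---|---|---|---|
| 1 month | 5 months | 0.0102 | 6.1 | 29.3% | 9.1% | 20.2 | 4.15 |
| 1 month | 4 months | 0.0127 | 7.6 | 29.1% | 8.8% | 20.3 | 4.23 |
| 3 months | 5 months | 0.0303 | 18.2 | 27.8% | 7.2% | 20.6 | 4.98 |
| 3 months | 4 months | 0.0377 | 22.6 | 27.3% | 6.5% | 20.8 | 5.42 |

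Of the 60 expected Group 2 successes (10% of 600), the affected women are 10–13% at 1 month and 30–38% at 3 months. Of the 180 in Group 1 (30% of 600), they are 3–4% and 10–13%. Power after removal stays above 99% (t, 8 df).

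**5. Extreme difference between arms.** If every gap-tested woman were removed in Group 1 and none in Group 2, the difference would be 19.1–19.3 points at 1 month and 17.3–17.8 at 3 months. In the reverse case it would be 20.9–21.2 and 22.8–23.5. The lowest power in the unfavourable case is 97.6% (t, 8 df).

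**6. Do gap tests fall in the outcome window?** Table 3 puts reminders and randomization in Year 1 Q3–Q4. A 4–5 month wait therefore ends near or after the start of Year 2, and sampling and letters sit under the Year 2 heading. Most gap tests should fall in Year 2. One that falls before Year 2 starts would count only under the wider wording in Measures, which refers to screening during the project.

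**The case against.** The best defence is that these women were properly eligible. They met criterion c at identification and again when the frame was built. As the document is ordered, randomization precedes sampling, so a later clinic test is a post-randomization event that an intent-to-treat analysis of Year 2 screening may legitimately count. In Group 2 it is usual care working. Removing such women takes events out of the analysis and, if mailing were slower in one arm, would take more from that arm.

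This stands in part. It would be wrong to call these women never eligible, and a rule that counted every test from sampling onward would be coherent. The plan does not follow that rule either, because it removes the women who reply. The risk of uneven removal is a reason to run the check on the same schedule in both arms and to report a sensitivity analysis.

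The inputs also lean high, and this objection stands. The letter exists to catch these women, so universal silence is a worst case. The 5% is a response to a fresh reminder, whereas the gap contains only women who did not respond to it. A long general gap has no support in Table 3, which starts both arms' activity in Year 2 Q1.

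Finally, the letter is in an appendix and the process figure is not shown. The finding is that no re-check is described in the available text, not that none could exist.

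**Conclusion.** The inconsistency is real: under the stated rules the same gap test is an exclusion or a success depending on a posted reply. Its expected effect is a modest attenuation of the odds ratio. At the upper bound, about 6–8 women per 600 are affected per month of gap. Removing them in both arms moves the OR from 3.86 to about 4.2 at 1 month or 5.0–5.4 at 3 months, and the risk difference by under 1 point. These figures rest on the assumptions listed in the working, above all the gap length, which the plan does not give.

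Three stronger readings are tempting, and the documents do not support them.

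- **Bias between arms.** A reader might infer that the rule favours one arm. The confirmation procedure is the same in both, and the letter precedes the kit or second reminder. Bias in either direction would need reply rates or gap length to differ by arm, which nothing in the documents shows.
- **Gap tests on top of 30% and 10%.** A reader might add gap tests to these figures and conclude that the OR falls below 3.86. But they are the expected Year 2 proportions, and the record review counts any Year 2 clinic test, so countable gap tests are already inside them. Adding a 6-month gap at 10% per year would give Group 2 a rate of 1 − 0.9^1.5 = 14.6%, which is 18 months of testing in a 12-month year.
- **Power.** It is not at risk in any case shown.

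**What to change.** In both arms and on the same schedule, have clinic staff repeat the EHR query for criterion c on the sampled women just before the kit or second reminder is mailed. Drop and replace any woman with a test since the frame was built, whether or not she returned the letter. Keep the letter for criteria that the EHR cannot show.

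Do the same for the Year 3 draw, where the Year 2 method and its silence rule still apply. From Year 4 a completed form must be returned, which largely covers the point.

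For the primary outcome, count clinic tests from each woman's mailing date. Report pre-mailing removals by arm, and add a sensitivity analysis that keeps women with pre-mailing tests. This requires their test dates and outcomes to be retained.

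The cost is one repeat, on about 1,200 women in Year 2 (2 × 600), of a query the clinics already run, and a few more replacements.

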Women who have not returned their HPV self-test within two weeks of the device being sent will receive PN for self-test return. PNs will attempt to contact these initial non-returners by text message and/or telephone, making up to 10 attempts at different times and on different days, including weekends. If no contact is made after the final attempt, PNs will send women a letter asking them to contact the PNs (see Appendix). Using a similar approach, PNs contacted almost 90% of participants in our past work.³⁴ During interactions with participants, PNs will apply their training to provide information about HPV and self-testing, address women's concerns and barriers to using/returning their self-test, help women set goals and plans for using/returning their self-test, and provide social support. PNs will also ask women if they need a replacement device sent. To ensure consistency in the process, PNs will use developed guides/scripts during calls and text messages (see Appendices). If a woman has already returned her self-test by the time of contact, the PN will ask if she had any questions. Members of the study team will not have direct contact with any of the participants, only the PNs (who are employees of the clinics) will contact participants or have access to participants' contact information.

PNs will contact each of these initial non-returners at least once about using/returning their self-test, with additional contacts as needed (e.g., if PNs need to locate further information after the first contact). This will allow PNs flexibility that is tailored to each woman's needs. Following completion of PN (or final contact attempt without success and a letter sent), we will give women two additional weeks to return their HPV self-test. All women who do not return their self-test following this additional time will be classified as having not returned their HPV self-test.

HPV Testing

All returned HPV self-tests will be sent to a laboratory at Atila BioSystems (Mountain View, CA) for HPV testing. The laboratory has expertise in HPV testing and has performed this type of testing extensively in the past. Testing will use the Atila AmpFire HPV test, which produces one of the following outcomes for each sample: (a) positive for high-risk HPV type 16 or 18; (b) positive for a high-risk HPV type other than type 16 or 18 (i.e., type 31, 33, 35,

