39, 45, 51, 52, 53, 56, 58, 59, 66 or 68); (c) negative for high-risk HPV types; or (d) inadequate sample. The detectable high-risk HPV types cause almost all cervical cancers. We do not expect “inadequate sample” to occur often since all women in our pilot study collected adequate samples,²⁴ but will send a replacement device for resampling if it does occur. The laboratory will send HPV testing results to the project team via secure email and using only participant ID numbers. Results will be available within about a month after a sample is sent to the laboratory. All HPV testing results will be entered into a database by the project team (see Appendix).

Notification of Results to Clinics

Upon receipt of HPV testing results, we will notify a designated person at each clinic (e.g., the PN) of the results for each participant (using only participant ID numbers). This notification will occur via secure email. The notification email (see Appendix) will be patterned after a similar communication in our past HPV self-test work (IRB# 2015C0036) and contain: a) HPV testing results for participants; b) an interpretation of the results; and c) contact information for the project team in case there are any questions.

Notification of Results to Women

The clinics will then mail a notification letter to each participant (see Appendix). The notification letter will include HPV testing results and an interpretation of the results. The letter will indicate appropriate next steps based on the HPV testing results. For women who test negative for high-risk HPV types, the letter will indicate that no follow-up care is needed at this time. For women who test positive for high-risk HPV types, the letter will indicate that someone from their clinic (e.g., PN) will contact them in the next few days to help schedule a follow-up appointment. Contact information for the clinic will be provided in this letter.

Patient Navigation for Follow-Up Appointment

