The patient-level effectiveness outcome and primary outcome for our project will be whether or not women get "screened" during the project. There are three ways a woman can be considered "screened." The first is to return their HPV self-test and test negative for high-risk HPV types. The second is to return their HPV self-test, test positive for high-risk HPV types, and then attend a follow-up appointment at their health system. We are requiring these women to attend a follow-up appointment to be considered "screened" given their HPV infection. The third way is to receive a clinic-based screening test (e.g., Pap test), regardless of HPV self-test return status. This will most likely apply to women in Group 2 health systems during the Usual Care Continued phase, but past studies have shown that some women will get a Pap test after receiving an HPV self-test in the mail (without using the self-test).⁴² All women not meeting one of these three criteria will be considered "unscreened." To determine this outcome, we will examine HPV self-test return status, HPV testing results, and EHR data (follow-up appointment attendance, Pap testing, etc.) for each sampled woman.

Among women who return their HPV self-test, we will examine the timing of device return and categorize each as returned within two weeks of distribution (i.e., prior to any PN) or after two weeks of distribution (i.e., following PN). We will also examine HPV testing results (positive or negative for high-risk HPV types) and collect data from EHR on the number of normal and abnormal clinic-based cervical cancer screening tests received by each woman and any cervical abnormalities found (i.e., low-grade squamous intraepithelial lesion, etc.).

To assess if the intervention is equitable (Figure 4), we will examine patient characteristics via data from HER (e.g., age and when their most recent clinic-based cervical cancer screening test prior to project entry occurred [if

ever]). Lastly, to assess safety, we will examine data from the patient satisfaction survey to see if women report any issues about using their HPV self-test. We do not anticipate such reports to be common, as HPV self-test devices have been used safely and easily by women in several research studies.⁶⁻¹⁵

Sample Size

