The project's total sample size will be 1800 women across Years 2-5 (900 women from Group 1 clinics/health systems and 900 from Group 2 clinics/health systems). These sample sizes are feasible given the expected sampling frame size (see Table 1) and will give us at least 90% power for the below analyses.⁴³ The power calculation assumed a two-sided alpha=0.05, an intraclass correlation coefficient<0.017 (based on our pilot study), and the below outcome occurrences.

Primary Analyses

Primary analyses will examine the proportion of women from Year 2 screened, as defined above, and use an intent-to-treat approach. To compare treatment groups (Group 1 vs. Group 2), we will use generalized linear mixed models (GLMMs) to account for the correlation between women from the same clinic,⁴⁴ though we expect cluster effects to be low (i.e., intraclass correlation coefficient<0.017 based on our pilot study). Since our outcome is binary, we will use a logit link to estimate odds ratios for the GLMMs. We expect that 30% of women from Group 1 clinics/health systems and 10% of women in Group 2 clinics/health systems will be categorized as screened. The primary model will be unadjusted, but we will conduct sensitivity analysis that include potential confounders due to imbalance from randomization ($p<0.10$ when comparing groups). Results will determine the effectiveness of the intervention in increasing cervical cancer screening compared to usual care.

Secondary Analyses

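### No captured test is scored as unscreened, but only Group 1 has a route to success that bypasses the EHR, so incomplete EHR capture may inflate the primary odds ratio

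*Combined protocol and SAP*

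**What the plan says.** All references are to section 3 (Methods) of the combined protocol and SAP.

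- **Outcome definition (Aim 1, Measures).** A woman is screened by (a) a returned kit that is negative, (b) a returned kit that is positive plus follow-up attended at her own health system, or (c) a clinic-based test, with no limit stated on where it is done. Then: "All women not meeting one of these three criteria will be considered" unscreened. There is no category for a record that could not be reviewed.
- **Kit results (HPV Testing).** "The laboratory will send HPV testing results to the project team via secure email and using only participant ID numbers". In Year 2 kits go to Group 1 only; Group 2 receives another reminder letter and an information sheet.
- **Clinic-based tests and follow-up (Data Collection for Year 2, Medical Record Review).** "We will work with the each health system to gather data from EHR". The review for clinic-based tests covers both groups, and clinic staff enter the data. No claims data, outside records or patient report is named as a further source.
- **Analysis (Primary Analyses).** The effect is an odds ratio from a logistic mixed model. The expected result is that "30% of women from Group 1 clinics/health systems and 10% of women in Group 2 clinics/health systems" will count as screened. The one sensitivity analysis planned for this model concerns baseline imbalance.

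**The concern.** Scoring an unobserved outcome as failure is usually defended as conservative. Here it need not be. A negative kit cannot be lost through a gap in the EHR, but a Pap test in Group 2 can. If some clinic-based tests never reach the record that is reviewed, the control rate falls by the full proportion lost, while the intervention rate falls only in its EHR-dependent part.

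Some loss is plausible on the plan's own terms. One visit in two years makes a woman an active patient, so care elsewhere is possible. The eligibility letter lets women correct the record at entry, but nothing equivalent covers tests received during Year 2. Route (c) as worded also admits a test done elsewhere, which the named data source may not show.

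At stake are the size of the primary effect and, where the risk difference is affected, the cost per additional woman screened in the Cost-effectiveness section.

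**Working it through.** **1. The plan's own figure.** Sample Size says the numbers "will give us at least 90% power for the below analyses". Inputs: two-sided alpha 0.05; ICC below 0.017 (0.017 used); 30% against 10%; 600 women per group in Year 2 ("We will sample a total of 600 women across Group 1 health systems", and the same for Group 2); five health systems per group, so 120 women per system if sizes are equal.

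- Design effect = 1 + (120 − 1) × 0.017 = 3.023. Effective n = 600 / 3.023 = 198.5 per group.
- Standard error = √[(0.30×0.70 + 0.10×0.90) / 198.5] = 0.0389. z = 0.20 / 0.0389 = 5.14.
- Power is 99.9% (normal reference) or 99.4% (t, 8 df). The stated minimum is met.
- Planned OR = (0.30/0.70) / (0.10/0.90) = 3.86.

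**2. Model for capture.** Let s be the probability that the EHR shows a clinic-based test or follow-up visit that took place, equal in both groups. Let L be the part of Group 1's 30% established by the laboratory alone. Working back from the planned observed rates:

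- true Group 1 rate = L + (0.30 − L)/s
- true Group 2 rate = 0.10/s

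The documents give neither s nor L. I assume s from 0.5 to 1 and L from 20 to 30 points. The upper part of the range for L fits the plan's remark that route (c) will apply mostly to Group 2.

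**3. True values behind an observed 30% against 10% (OR 3.86, difference 20 points).**

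| s | True OR, L = 30 / 25 / 20 | True difference in points, L = 30 / 25 / 20 |
|---|---|---|
| 0.9 | 3.43 / 3.52 / 3.61 | 18.9 / 19.4 / 20.0 |
| 0.8 | 3.00 / 3.18 / 3.37 | 17.5 / 18.8 / 20.0 |
| 0.6 | 2.14 / 2.50 / 2.89 | 13.3 / 16.7 / 20.0 |
| 0.5 | 1.71 / 2.15 / 2.67 | 10.0 / 15.0 / 20.0 |

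Example, s = 0.8 and L = 25: Group 1 = 0.25 + 0.05/0.8 = 0.3125; Group 2 = 0.10/0.8 = 0.125; OR = 0.4545/0.1429 = 3.18.

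**4. Where the direction changes.** Setting the true OR equal to 3.86 and solving for L gives 7.2 points at s = 0.9, 7.9 at 0.8, 9.7 at 0.6 and 10.9 at 0.5. Above those values the OR is inflated.

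The true risk difference is L + (0.20 − L)/s. It equals 20 points when L = 20, that is, when Group 1's EHR-dependent share equals Group 2's 10 points. With L = 22 and s = 0.8 it is 32.0 − 12.5 = 19.5, a bias of half a point. With L = 18 it is 20.5 at s = 0.8 and 21.3 at s = 0.6, so the trial would understate it.

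**5. Effect on significance.** In the worst case (L = 30) the true Group 1 rate stays at 30%. With the design effect of 3.023, the contrast stops being significant when the true Group 2 rate reaches 21.45% (normal reference; s = 0.10/0.2145 = 0.47) or 20.0% (t, 8 df; s = 0.50).

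**The case against.** The strongest reply is that the same EHR review for clinic-based tests applies to both groups, that Group 1's routes (b) and (c) depend on the EHR too, and that nothing in the documents says capture is incomplete or that the EHR leaves out outside results. All of that stands. It limits the claim to a possible bias of unknown size. It does not remove the asymmetry, because route (a) has no counterpart in Group 2 in Year 2.

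Two rules can also lower Group 1. A kit not returned within two further weeks after navigation ends is classed as not returned, and follow-up after a positive kit is tied to the woman's own health system. Neither is in the calculation above, so the net direction is less certain than the table alone suggests.

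A reader might infer three stronger points that the documents do not support:

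- **That the risk difference always favours the intervention.** It does so only below the 10-point threshold in step 4.
- **That navigators give Group 1 a second channel for reporting outside tests.** The plan does say "PNs will attempt to contact these initial non-returners by text message and/or telephone", and navigators are clinic staff. But recording outside tests is not among their listed tasks, and the outcome sources named are return status, laboratory results and EHR data. No figure can be put on this.
- **That the primary conclusion is in doubt.** At the planned 20-point gap it is not, unless capture is very poor.

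**Conclusion.** The concern holds as a possible upward bias in the primary odds ratio, of unknown size, with no analysis planned to bound it. Assuming equal capture in both groups and 20 to 30 laboratory-only points, the reported OR would be 1.07 to 1.29 times the true one at 80 to 90% capture, and up to 2.25 times at 50%. The risk difference may be inflated, unbiased or understated, depending on a route split that the plan does not give. The cost per additional woman screened follows it: with L = 30 and s = 0.8 the difference is 17.5 rather than 20 points, so for the same incremental cost the true figure would be 20/17.5 = 1.14 times the reported one. At the planned effect, the test result survives down to about 50% capture even in the worst case. The main risk is to the size of the effect, not to whether one is found.

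**What to change.** 1. **Measures and Medical Record Review.** State whether a clinic-based test done outside the health system counts. Determine route (c) with one identical EHR query (same codes, same dates, same outside-result fields) in all ten systems.
2. **Medical Record Review.** Record whether each woman's EHR could be reviewed to the end of Year 2. Report non-reviewable records by group and system. For women without a laboratory-established success, vary the outcome of those records in a sensitivity analysis. Imputing by group and system is not a substitute: a system that supplies no data has nothing to impute from, and a woman tested elsewhere may have a fully reviewable record.
3. **Primary Analyses.** Report the result by route (kit negative; kit positive plus follow-up; clinic-based test). Pre-specify a sensitivity analysis of the OR and the risk difference at, for example, 90%, 80% and 60% capture, and give the capture rate at which the lower confidence limit reaches no effect.

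Cost: SAP wording, one shared query, one extra field per woman and a few model runs. The reported effect may turn out slightly less favourable.
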